ICH	International Conference on Harmonisation
IMP	Investigational Medicinal Product
MedDRA	Medical Dictionary for Regulatory Activities
MGH	Massachusetts General Hospital
RTF	Rich Text Format
SAE	Serious adverse event
SAP	Statistical Analysis Plan
SC	Subcutaneous
SD	Standard deviation
SOP	Standard operating procedure
T1DM	Type 1 diabetes mellitus
VAS	Visual analog scale
WHO	World Health Organization

1. INTRODUCTION

This Statistical Analysis Plan (SAP) is based on the Zealand Pharma A/S ("Zealand") final protocol version 7.0 dated September 28, 2016. The SAP provides guidance for and description of the statistical methods and procedures to be implemented for the analyses of data collected within the scope of Clinical Trial Protocol ZP4207-16051.

Results obtained from the analysis outlined in this document will become the basis for the final Clinical Study Report (CSR) for this protocol. This SAP supersedes the statistical considerations identified in the protocol; where considerations are substantially different, they will be so identified. If additional analyses are required to supplement the planned analyses described in this SAP, they may be performed and will be identified in the CSR. Any substantial deviations from this SAP will be agreed upon between Zealand and Medpace and identified in the CSR. Any minor deviations from the tables/figures/listings (provided in a separate Programming Specifications document) may not be documented in the CSR, but will be noted within the Programming Specifications document.

2. TRIAL OBJECTIVES

2.1.1 Primary Objective

The primary objective of this trial is:

- To conduct a trial testing the safety and tolerability of the bionic pancreas (BP), using either the iLet or the iPhone platform, when used with ZP4207 in 20 adult (≥ 18 years of age) patients with type 1 diabetes mellitus (T1DM).

2.1.2 Secondary Objective

The secondary objectives of this trial are:

- To measure glycemic regulation, including hypoglycemia exposure (percent of time spent with continuous glucose monitor [CGM] glucose < 60 mg/dL).
- To evaluate BP device reliability.
- To document the satisfaction of patients with the BP with the goal of optimizing the functionality and user interface of the BP.

3. TRIAL OVERVIEW

3.1 Overall Trial Design and Treatment Assignment

[figure not shown]
This is a Phase 2 single-center, open-label, 2-part, randomized cross-over trial in adult patients (≥ 18 years of age) with T1DM. Patients who already manage their T1DM using continuous subcutaneous (SC) insulin infusion pump therapy will be enrolled. The trial will assess the safety and efficacy of the BP, using either the iLet or the iPhone platform, using the glucagon analog

ZP4207 versus Lilly glucagon. In Part 1, up to 10 patients will participate in two 1-day treatment arms in random order (iPhone-based BP using ZP4207 and iPhone-based BP using Lilly glucagon) according to the randomization scheme. In Part 2, up to 10 new patients will participate in two 1-day treatment arms in random order (iLet using ZP4207 and iLet using Lilly glucagon) according to the randomization scheme. The BP will also administer insulin (insulin lispro, Lilly Humalog) using the same blood glucose (BG) control algorithm for all 4 treatment arms. The trial will be conducted at the Massachusetts General Hospital (MGH) Diabetes Center in Boston, MA. Up to 40 patients will be enrolled in this trial with the expectation that up to 10 patients will complete each part of the trial.

[figure not shown]
The overall trial design is displayed in Figure 1.

Figure 1. Trial Design Schematic

Part 1:

Part 2:

Patients can only participate in 1 part of the trial.
 ADA = anti-drug antibodies, BP = bionic pancreas.

Patients who have completed the Screening Visit and meet all of the inclusion and none of the exclusion criteria will be enrolled. The order of the treatment visits will be randomized in blocks of 2 patients.

The schedule of events for the trial is provided in Table 1.

Table 1. SCHEDULE OF PROCEDURES – PARTS 1 AND 2

Trial Visit	Visit 1 [1] Screening	Visit 2 Training	Visit 3 [2] [3] [4] [5] (1 st Treatment Visit)	Visit 4 [2] [3] [5] (2 nd Treatment Visit)	Visit 5 ADA Assessment Visit [6]	Visit 6 Follow-Up [7]
Informed consent	X					
Assess/confirm eligibility	X	X				
Demographics	X					
Medical, surgical, and social history; allergies	X					
Concomitant illness	X					
Concomitant medications	X	X	X	X	X	X
Height, weight, physical examination, and vital signs including body temperature and blood pressure [8]	X		X [9]	X [9]		
12-lead ECG	X		X [10]	X [10]		
Urine HCG pregnancy test and menstrual history [11]	X		X	X		
FSH [12]	X					
Screening labs – HbA1c, optional fractionated metanephrines [13]	X					
Safety lab sampling including chemistry and hematology	X		X [10]	X [10]		X
Training on devices [14]		X				
Monitored BP use			X	X		
Plasma glucose sampling [15]			X	X		
ZP4207/glucagon exposure sampling [16]			X	X		
Nausea and infusion site pain VAS and infusion site reaction Draize scale (visit start [17], hourly, & visit end)			X	X		

Trial Visit	Visit 1 [1] Screening	Visit 2 Training	Visit 3 [2] [3] [4] [5] (1 st Treatment Visit)	Visit 4 [2] [3] [5] (2 nd Treatment Visit)	Visit 5 ADA Assessment Visit [6]	Visit 6 Follow-Up [7]
Standardized lunch [18]			X	X		
In-clinic exercise [19]			X	X		
Questionnaires (pre & post BP)			X	X		
ADA			X [20]		X	X
Adverse event review			X	X	X	X

1. Once the patient has been enrolled and eligibility has been established, the order of the treatment visits will be randomized in blocks of 2 patients.
 
2. In Part 1, each patient will participate in 2 treatment visits: 1 with the iPhone-based BP using ZP4207 and 1 with the iPhone-based BP using Lilly glucagon in a randomized order. In Part 2, each patient will participate in 2 treatment visits: 1 with the iLet using ZP4207 and 1 with the iLet using Lilly glucagon in a randomized order. Up to 2 patients may participate in the trial per day.
 
3. The night before the visit, patients will place a Dexcom G4 CGM sensor in the abdominal skin and calibrate the sensor when prompted using the provided Nova StatStrip Xpress meter. Patients will be asked to arrive at the visit at least 1 hour in advance of the start of the BP having fasted since 12:00 AM the night before (treatment with simple carbohydrate of up to 30 g for a low is allowed). If the patient is not fasted, the visit will be rescheduled within the visit window. If BG is >250 mg/dL, the visit will be rescheduled within the visit window. If BG is <50 mg/dL, treatment with simple carbohydrate is allowed. If the patient experiences persistent hypoglycemia, the visit will be rescheduled within the visit window.
 
4. Visit 3 will take place at least 48 hours after screening (Visit 1) and no more than 30 days after screening (Visit 1).
 
5. There will be a 24-hour minimum washout between Visit 3 and Visit 4 and a maximum of 3 weeks between Visit 3 and Visit 4.
 
6. Visit 5 will take place 10 days ±3 days from Visit 4.
 
7. Visit 6 will take place 25 days ±4 days from Visit 4.
 
8. Height and physical examination will be measured at Visit 1 only.
 
9. Vital signs including body temperature and blood pressure will be obtained at visit start and visit end.
 
10. At visit start and visit end.
 
11. Urine HCG pregnancy test only for women of childbearing potential. The date of the last menstrual period in female patients will be obtained at Visit 1 only.
 
12. Test for FSH level only for postmenopausal women amenorrheic for less than 1 year.
 
13. If indicated by history.
 
14. Patients will be trained in the insertion and calibration of the Dexcom G4 sensor, diabetes management (e.g., basal insulin rate adjustment by insulin pump) during fasting prior to and between the treatment visits, and trial policies and procedures.
 
15. Collected at least hourly. If BG is <150 mg/dL, then sampling will be every 30 minutes. If BG is <100 mg/dL, then sampling will be every 20 minutes. If BG is <80 mg/dL, then sampling will be every 10 minutes.
 
16. Collected at least hourly. If BG is <150 mg/dL, more frequent samples for plasma ZP4207/glucagon may be drawn at the discretion of the Investigator.
 
17. Once the infusion sites have been placed but no drug has yet been administered.
 
18. Between approximately Hour 3 and Hour 4.
 
19. Between approximately Hour 6 and Hour 7.
 
20. Before the start of dosing.
 
ADA = anti-drug antibodies; BG = blood glucose; BP = bionic pancreas; CGM = continuous glucose monitor; ECG = electrocardiogram; FSH = follicle-stimulating hormone; HbA1c = hemoglobin A1c; HCG = human chorionic gonadotropin; VAS = visual analog scale.
						

3.2 Trial Endpoints

3.2.1 Primary Endpoint

The primary endpoint is the safety and tolerability of ZP4207 in the BP using either the iLet or the iPhone platform as assessed by

- Number and type of adverse events (AEs)
- Clinical laboratory measurements
- Vital signs
- 12-lead electrocardiograms (ECGs)
- Local tolerability and infusion site reactions as measured with the Draize scale
- Immunogenicity as measured by anti-drug antibodies (ADA)
- Pain as measured on a 10 cm visual analog scale (VAS)
- Nausea as measured on a 10 cm VAS

3.2.2 Secondary Endpoints

The secondary endpoints include measurements of BP function as well as glycemic and non-glycemic measurements.

3.2.2.1 Bionic Pancreas Function Endpoints

This endpoint data will be generated from the BP data during each treatment visit:

- Average percent insulin dose amounts calculated by the BP control algorithm that are successfully delivered by the pump
- Average percent glucagon/ZP4207 dose amounts calculated by the BP control algorithm that are successfully delivered by the pump
- Average percent dose amounts successfully issued to the pump by the BP control algorithm that are successfully delivered by the pump (calculated doses are not issued unless the pump is accessible and its delivery channel is available)
 - Average percent insulin dose amounts successfully issued to the pump by the BP control algorithm that are successfully delivered by the pump
 - Average percent glucagon/ZP4207 dose amounts successfully issued to the pump by the BP control algorithm that are successfully delivered by the pump
- Average percent dose amounts calculated by the BP algorithm that are successfully issued to the pump by the BP (calculated doses are not issued unless the pump is accessible and its delivery channel is available)
 - Average percent insulin dose amounts calculated by the BP control algorithm that are successfully issued by the BP
 - Average percent glucagon/ZP4207 dose amounts calculated by the BP control algorithm that are successfully issued by the BP
- Average percent of 5-minute steps during which the BP is functioning nominally in all respects based on real-time CGM data (meaning a new CGM glucose reading is captured, the dose is calculated, and the dose is issued to the pumps)
- Average percent of 5-minute steps during which the BP is functioning nominally with or without a new CGM glucose reading captured (meaning the dose is calculated and issued to the pumps). If a CGM signal is not available, the dose calculated may be based on weight or historical basal rates.
- CGM reliability index (calculated as the percent of possible values actually recorded by the CGM)

- CGM Mean Absolute Relative Difference versus time-stamped BG values from meter download
- List of technical faults associated with the BP including cause and resolution

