3.2.2.2 Glycemic Endpoints

All of the following metrics will be generated from the Dexcom G4 Platinum CGM data during each treatment visit:

- Fraction of time spent within each of the following glucose ranges:
 - <50 mg/dL
 - <60 mg/dL
 - <70 mg/dL
 - 70-120 mg/dL
 - 70-140 mg/dL
 - 70-180 mg/dL
 - >180 mg/dL
 - >250 mg/dL
 - >300 mg/dL
- Number of severe hypoglycemic events (patients unable to self-treat, requiring the assistance of another person)
- Number of episodes of symptomatic hypoglycemia
- Number of carbohydrate interventions for hypoglycemia
- Total grams of carbohydrates taken for hypoglycemia
- Mean CGM glucose

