4.7.2 Glycemic Endpoints

Similar analysis, as described previously for the BP function endpoints, will be performed for the plasma glucose measurements.

The number of patients and the proportion of patients with severe hypoglycemia events, symptomatic hypoglycemia, and carbohydrate interventions due to hypoglycemia will be summarized descriptively. The number of events will also be summarized. The proportions will be analyzed by a Fisher's exact test, if data allow. The sample SAS code for the analysis involving the proportion of subjects that had a carbohydrate intervention due to hypoglycemia is included here:

```
.....  
Note: treatment = treatment group (1=Lilly glucagon, 2=ZP4207)  
carb = subject had a carbohydrate interventions due to  
hypoglycemia (Yes or No).  
.....  
proc freq ;  
tables treatment*carb / fisher ;  
run;  
.....
```

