5. SAMPLE SIZE DETERMINATION

No formal sample size calculations were made. It is expected that between 20 and 24 patients will be randomized in the trial. The sample size is based on a clinical rather than statistical rationale. The sample size is considered adequate to address the primary trial objective of

exploring the safety of ZP4207 when used in the BP and with reference to Lilly glucagon used in the BP.

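### CGM accuracy (MARD) is referenced to meter glucose, apparently from the meter that calibrates the sensor, although plasma glucose is drawn at least hourly and would be a better reference

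*SAP*

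**What the plan says.** - **Reference for MARD.** SAP Section 3.2.2.1 lists "CGM Mean Absolute Relative Difference versus time-stamped BG values from meter download" among the bionic pancreas (BP) function endpoints, which are to come from data generated during each treatment visit. The meter is not named. Nothing is said about calibration readings or about how CGM and meter values are paired in time.
- **Calibration.** In Section 3.1, Table 1, footnote 3, patients place the sensor the night before the visit and "calibrate the sensor when prompted using the provided Nova StatStrip Xpress meter". No other meter is named in the SAP.
- **Plasma glucose.** Table 1 schedules it at both treatment visits. Footnote 15 gives the frequency: "Collected at least hourly. If BG is <150 mg/dL, then sampling will be every 30 minutes", then every 20 minutes below 100 mg/dL and every 10 minutes below 80 mg/dL.
- **Planned use of plasma glucose.** Section 4.7.2 states: "Similar analysis, as described previously for the BP function endpoints, will be performed for the plasma glucose measurements". No section uses it to judge the sensor.
- **What rests on the sensor.** Section 3.2.2.2 introduces the glycemic endpoints with "All of the following metrics will be generated from the Dexcom G4 Platinum CGM data during each treatment visit".

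**The concern.** An accuracy measure needs a reference that does not share errors with the device under test. If one meter both calibrates the sensor and serves as the reference, a systematic meter error enters the sensor at calibration and then drops out of the comparison. Any calibration reading counted as a pair also compares the sensor with the value to which it has just been set.

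MARD is the only sensor-accuracy measure listed under the device-reliability objective in Section 2.1.2; the CGM reliability index measures only data capture. The same CGM informs dosing and generates the time-in-range fractions, including time below 60 mg/dL, which Section 2.1.2 names. A calibration bias would shift those fractions, and the planned MARD would not reveal it.

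**Working it through.** The SAP states no MARD figure, target, meter error or sensor error, so there is nothing to reproduce. All error sizes below are assumptions, chosen to show how the two references behave.

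**1. Variance argument, calibration readings excluded.** Assume sensor noise 10%, meter random error 5%, plasma error 2%, and a sensor that inherits the mean error of two calibration readings. Meter bias varies between patient-visits with SD b (in %). For roughly normal relative errors, MARD ≈ √(2/π) × SD = 0.798 × SD.

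- Against the same meter the bias cancels. Variance = 10² + 5²/2 + 5² = 100 + 12.5 + 25 = 137.5, so MARD ≈ 0.798 × 11.73 = 9.4%.
- Against plasma the bias remains. Variance = 10² + 5²/2 + b² + 2² = 116.5 + b².

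| Bias SD b | MARD vs meter | Variance vs plasma | MARD vs plasma |
|---|---|---|---|
| 0% | 9.4% | 116.5 | 8.6% |
| 3% | 9.4% | 125.5 | 8.9% |
| 5% | 9.4% | 141.5 | 9.5% |
| 8% | 9.4% | 180.5 | 10.7% |

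The two are equal when 116.5 + b² = 137.5, so b = √21 ≈ 4.6%. Below that, meter-referenced MARD is the higher figure; above it, the lower. The meter column does not respond to b at all. That is the defect, and it does not depend on the sign of the net difference.

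**2. Simulation with a fixed meter bias** (400,000 pairs per setting). Sensor CV was 10% or 14%, bias ran from -10% to +10% and was fully inherited by the sensor, meter CV was 2%, 5% or 7%, and plasma CV was 2%. This model omits the inherited random calibration error of step 1. At sensor CV 10%:

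| Bias | Meter CV | MARD vs meter | MARD vs plasma | Difference (points) |
|---|---|---|---|---|
| 0 | 5% | 8.9% | 8.1% | +0.8 |
| 0 | 7% | 9.8% | 8.1% | +1.7 |
| +5% | 2% | 8.1% | 9.5% | -1.3 |
| +5% | 7% | 9.8% | 9.4% | +0.4 |
| +10% | 2% | 8.2% | 12.3% | -4.2 |
| +10% | 5% | 8.9% | 12.3% | -3.3 |

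Differences were taken before rounding. Over the whole grid they run from -4.2 to +1.7 points.

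**3. Calibration readings counted as pairs.** Assume sensor error of 12% in general and 3% just after calibration. MARD is then 0.798 × 12 = 9.6% and 0.798 × 3 = 2.4% respectively.

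- 10% calibration pairs: 0.9 × 9.6 + 0.1 × 2.4 ≈ 8.9%.
- 20% calibration pairs: 0.8 × 9.6 + 0.2 × 2.4 ≈ 8.1%.

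This effect always lowers MARD, but the share of such pairs cannot be read from the SAP.

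**4. Sampling density.** Under footnote 15, an hour below 80 mg/dL gives 60/10 = 6 plasma samples, against a minimum of 1 per hour at 150 mg/dL or above. A pooled plasma-referenced MARD would therefore weight low glucose heavily, so results by range are needed beside the overall figure.

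**The case against.** A reader might infer that the plan understates sensor error, by perhaps 1 to 4 points. Such figures can be produced: with bias SD 3% and 2 calibration readings among 8 pairs, a simulation gives 8.0% against the meter and 9.0% against plasma; with bias SD 8% and 2 among 4 pairs, 6.7% and 10.8%. But they assume that a quarter to a half of all pairs are calibrations. Section 3.2.2.1 limits the data to the treatment visit, and the calibration described in footnote 3 begins the night before. Calibration when prompted could also fall within the visit, but none is scheduled. Without those pairs the sign at bias SD 3% reverses (9.4% against 8.9%). This part of the objection stands.

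It also stands that several links are inferences. The SAP does not say that the MARD meter is the calibration meter, that meter samples are fingersticks, or how plasma glucose is assayed. The protocol may settle these, and the pairing rules could sit in the derived-database specifications of Section 6.2.

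Impact is limited too. The primary endpoint is safety and tolerability. Both crossover arms use the same sensor and reference procedures, so the comparison of ZP4207 with glucagon is not obviously distorted. Changing the reference alters no glycemic result, and plasma glucose is analyzed separately.

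None of this removes the core point. The SAP itself names the reference, and a probably better one is scheduled at the same visits.

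**Conclusion.** The point holds as a cheap improvement of limited impact. As written, MARD is probably not independent of sensor calibration and cannot show meter bias passed to the sensor. This rests on two assumptions: that the downloaded meter is the calibrating one, which is likely because only one is named, and that the sensor takes on meter bias through calibration.

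The documents do not support a claim that sensor error is understated, nor any single magnitude. Shared bias and counted calibration readings lower the meter-based figure, random meter error raises it, and the SAP gives no size for any of them. The range of -4.2 to +1.7 points is illustrative and covers only the first and last of these effects. No decision or threshold is attached to MARD.

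**What to change.** Confirm first that plasma glucose is assayed on a device separate from the calibrating meter. Then replace the bullet in Section 3.2.2.1 with wording such as:

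> CGM MARD versus time-matched plasma glucose collected during BP use at each treatment visit, overall and descriptively by plasma glucose range (<70, 70-180, >180 mg/dL). Each plasma value is paired with the nearest CGM value within a prespecified window. Supportive: CGM MARD versus downloaded meter values, with the meter named and any reading entered as a calibration excluded.

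The window should be set before database lock; one 5-minute BP step is a natural choice.

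The cost is SAP wording and one time-matching step on data already scheduled. With up to 10 patients per part and the parts analyzed separately, the extreme ranges may be sparse and should stay descriptive. The reported MARD may look less favorable than the meter-based one.

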3.2.2.2 Glycemic Endpoints

All of the following metrics will be generated from the Dexcom G4 Platinum CGM data during each treatment visit:

- Fraction of time spent within each of the following glucose ranges:
 - <50 mg/dL
 - <60 mg/dL
 - <70 mg/dL
 - 70-120 mg/dL
 - 70-140 mg/dL
 - 70-180 mg/dL
 - >180 mg/dL
 - >250 mg/dL
 - >300 mg/dL
- Number of severe hypoglycemic events (patients unable to self-treat, requiring the assistance of another person)
- Number of episodes of symptomatic hypoglycemia
- Number of carbohydrate interventions for hypoglycemia
- Total grams of carbohydrates taken for hypoglycemia
- Mean CGM glucose

3.2.2.3 Non-glycemic Endpoints

- Glucagon/ZP4207 total delivery per kg of body mass
- Insulin total delivery per kg of body mass
- Number of unscheduled infusion set replacements
- Number of unscheduled CGM sensor changes

4. STATISTICAL METHODOLOGY

4.1 Baseline, Endpoint, and Other Statistical Considerations

The clinical statistical analyses will be performed by Medpace.

Descriptive summary statistics including number (n), mean, median, standard deviation (SD), and range (minimum, maximum) for continuous variables (interquartile range [25th, 75th percentile] for non-parametric tests), and counts and percentages for categorical variables will be used to summarize data, as appropriate. Where appropriate, p-values will be reported. All statistical tests will be conducted using 2-sided tests with 5% significance level and 95% confidence interval, unless otherwise stated.

For all analyses, the 2 treatment arms from Part 1 (iPhone-based BP) will be compared, and the 2 treatment arms from Part 2 (iLet) will be compared. The analyses of Part 1 will be completely separate from the analyses of Part 2.

All data will be listed in patient-level data listings.

4.2 Analysis Populations

The following analysis populations are defined:

The Safety Analysis Set will consist of all patients who receive at least 1 dose of investigational medical product (IMP).

The Full Analysis Set (intent-to-treat population) will consist of all randomized patients. In exceptional cases, patients from the Full Analysis Set may be excluded (will be decided in the database review [DBR] meeting). In such cases, the exclusion will be justified and documented.

The Per-Protocol Set will include all patients of the Full Analysis Set who completed the trial without any major protocol violations that may interfere with the assessment of drug efficacy.

Analyses of efficacy endpoints will be based on the Full Analysis Set (and Per-Protocol Set if necessary). This decision will be made in the DBR meeting. The analysis of the safety endpoints will be based on the Safety Analysis Set.

Before data are released for statistical analysis, a blinded review of all data will take place to identify protocol deviations that may potentially affect the results. At this time, it will be determined if patients and/or data should be excluded from the analysis. Furthermore, outliers will be identified by data review according to International Conference on Harmonisation (ICH) Guidance E9.

Obviously erroneous data points may be excluded from the analyses or re-analyzed (e.g., serum concentrations). The decision to re-analyze or exclude data points from the statistical analysis is the joint responsibility of the Sponsor, the Principal Investigator, and the Trial Statistician.

The patients or observations to be excluded and the reason for their exclusion will be documented and signed by those responsible prior to database release. The documentation will be stored together with the remaining trial documentation. The patients and observations excluded from analysis sets, and the reason for this, will be described in the clinical trial report.

